3. STUDY DESIGN

This pilot is a controlled mixed methods feasibility trial.

The Radboudumc department REshape & Innovation Center in collaboration with two physiotherapy departments will execute the pilot. The envisioned duration of the project is five months. Patients will be included in April and May 2018, after which we will analyse data and publish results. The product-testing period is 4 weeks per patient. There will be an intervention group and a control group. The control group will only execute point 1 and 5 in the research design described below besides their regular treatment (excluding interview and SUS component). The control group is present to exclude conclusions based on treatment effects instead of intervention effects. The intervention group will go through all five steps. Millen et al. chose a similar study design, where they measured self-efficacy in cardiac rehabilitation (Millen *et al.*, 2009).

In the present course of therapy, supporting their home exercise program, patients suffering from Neuralgic Amyotrophy or a lower extremity amputation (using a socket or an osseointegrated prosthesis) receive a folder with written instructions on performing the exercises which can be consulted when needed. Patients give feedback during every hospital visit regarding their exercises and progression. In these sessions, the physiotherapist asks for information on the whole week schedule, whereas for patients it is hard to remember the exercises of the beginning of the week. To improve this, the osseointegrated prostheses patients keep a daily paper-based diary for pain scale, pain location, prosthesis wearing time and time spent on muscle exercises and standing or walking. Apart from this, patients do not register or monitor their progress in current course of therapy.

The introduction of the sticky reminders in combination with the app alters the method of registration compared to the present course, but the overall process remains the same. *Instead of written or spoken instructions and feedback, this information will be digitally provided and available.*

The patient process is described and depicted below.

1. **Baseline measurement:** To monitor self-efficacy patients are asked to fill out a validated self-efficacy questionnaire. This outcome is supposed to be the baseline value of the pilot. For extra information regarding the patient, demographic questions will be included in the questionnaire.

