2. **Technology introduction:** In the first hospital visit, the patient will get all the necessary or desired information on the new technology. Following this meeting, patients have time to decide whether they want to participate in the pilot. After inclusion, patients receive help for installing the app and will get an introduction on how to use the application.
3. **Home registration:** After the regular physiotherapy appointment in the hospital, patients will receive exercises to execute in the home situation. These exercises are also linked to at least one NFC tag. These NFC tags are illustrated with a location, suitable for the exercises. Patients will discuss their personal appropriate locations for the NFC tags with their physiotherapist. When walking by the NFC tag, the patient can scan the tag with their personal smartphone, showing them a video of the corresponding exercise. All information that was previously provided in the folder is now handed to the patient via the video. The application registers the scanning of the tag on a secure server. If no prescribed exercises are performed within a predefined timeslot, the app will send a one-time push notification to the patient. At the end of the day, a tag will be scanned to show the daily report form. This daily report contains questions matching the regular treatment supplemented with questions on efficacy.
4. **Physiotherapy session:** Back in the hospital setting, the regular treatment is continued and the progress of the rehabilitation will be discussed. The app can support this session by presenting graphic representations of the daily feedback gathered with the daily reports. Step 3 and 4 will be repeated until the NFC tag trial period is over.
5. **Evaluation:** In the end, the questionnaire answered at the start is repeated as an end-measure, supplemented with a system usability scale (SUS) questionnaire. Elaborate opinions will be gathered by interviewing patients and physiotherapists in a semi-structured way. In semi-structured interviewing, a guide is used, with questions and topics that must be covered.

Sticking to your Exercises

[figure not shown]
However, in contrast to structured interviews, this conversational style of interviewing allows for gathering elaborate opinions.

The timeline is shown below. The control group and intervention group will undergo a different timeline:

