8.3 Study procedures

Patient's timeline

Patient timeline

The study flow and timeline are depicted above. After inclusion in the study, both the control and the study (intervention) group will fill in a questionnaire. This start-questionnaire will consist of questions regarding self-efficacy (ESES questionnaire) and demographics. Subsequently, they will either follow regular treatment (control) or receive our product and follow rehabilitation aided by the sticky reminders + app. After 4 weeks, the test period is over and patients will take part in evaluation. The evaluation for the control group consists of only one component: a questionnaire. This end-questionnaire is identical to the start-questionnaire and consists of questions regarding self-efficacy (ESES). For the intervention group, the evaluation consists of two components: a questionnaire and a semi-structured interview. This end-questionnaire consists of questions regarding self-efficacy (ESES) and system usability (SUS). The above described is summarized in the table below. The measurements and assessments are described in more detail under the headings “Parameter assessments” and “Measurements” below.

Physiotherapists’ assessment

The physiotherapists will fill in a questionnaire (SUS) and will be interviewed in a semi-structured way. The above described is summarized in the table below. The measurements and assessments are described in more detail under the headings “Parameter assessments” and “Measurements” below.

| Group | Start evaluation | End evaluation |
|-----------------|--|---|
| Control | Questionnaire: ESES + Demography | Questionnaire: ESES |
| Intervention | Questionnaire: ESES + Demography | Questionnaire: ESES + SUS Semi-structured interview |
| Physiotherapist | N/A | Questionnaire: SUS Semi-structured interview |

Parameter assessments

- Self-efficacy will be determined with the validated Dutch translation of the Exercise Self-Efficacy Scale and analysed with a social-cognitive model of health behaviour change theory. In this theory, self-efficacy is seen as a predictor, mediator or moderator (Burke *et al.*, 2008; Schwarzer, 2008) on health behaviour.
- Usability will be determined using the System Usability Scale, developed by J. Brooke, and by interviewing patients and physiotherapist in a semi-structured way based on a healthcare adapted UTAUT2 framework (Slade *et al.*, 2013).

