11.2 Recruitment and consent

First, eligible patients will be invited by their physiotherapists to participate in the pilot study. They will receive an information letter that explains the study in general. After a suitable period of time (1-2 weeks), follow-up telephone contact will explore whether subjects are interested, the purpose of the study and study procedures will be explained and interested patients will receive an extensive information package. The initial information letter and the informed consent form are attached as separate documents.

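### Sections 3, 8.3 and 11.2 order information, decision to participate and baseline ESES differently, and none places allocation; read literally, Section 3 gives only intervention patients a decision step

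*Protocol*

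**What the plan says.** Section 3 sets out the patient process in five numbered steps. Step 1 is the self-efficacy questionnaire: "This outcome is supposed to be the baseline value of the pilot". Step 2 is the technology introduction. It begins with information: "In the first hospital visit, the patient will get all the necessary or desired information on the new technology". The decision comes next: "Following this meeting, patients have time to decide whether they want to participate in the pilot". Practical help comes last: "After inclusion, patients receive help for installing the app and will get an introduction on how to use the application".

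The two groups follow different parts of this list. For controls: "The control group will only execute point 1 and 5 in the research design described below besides their regular treatment". For the others: "The intervention group will go through all five steps".

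Section 8.3 places the baseline elsewhere: "After inclusion in the study, both the control and the study (intervention) group will fill in a questionnaire".

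Section 11.2 describes recruitment without reference to group: "First, eligible patients will be invited by their physiotherapists to participate in the pilot study". An information letter, a telephone contact after 1-2 weeks and a fuller information package follow. This section mentions neither the technology meeting nor the baseline questionnaire.

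Section 4.2 requires consent in both groups, asks about an NFC-compatible phone when inclusion starts, and concedes that the study is not fully randomised for that reason. Section 8.2 promises randomisation as far as availability allows and rules out blinding. It does not say when allocation happens.

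**The concern.** The primary objective is a comparison with usual care on a self-reported scale, without blinding. In that setting the order of information, consent, baseline and allocation protects the comparison, and the protocol gives more than one order.

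Two things are at stake:

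- **Selection.** If only intervention patients decide after a meeting about the technology, those put off by it can leave that group before inclusion. Controls face no matching step. The intervention group could then be enriched for patients receptive to the app, in addition to the phone-ownership difference already admitted.
- **Baseline.** If the questionnaire is completed once a patient knows the group, the answers may reflect that knowledge, and the before-after change would carry it forward.

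Section 4.4 foresees using the pilot's data to size later randomised trials, so an unclear entry sequence could affect those trials too.

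**Working it through.** The protocol gives no figure on this point, so the check sets the sections side by side.

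| Source | Order given | Applies to |
|---|---|---|
| Section 3, steps 1-2 | Baseline ESES; technology information; decision; inclusion; app installation | Step 1 both groups; step 2 intervention only |
| Section 8.3 | Inclusion; baseline questionnaire; then usual treatment or the product | Both groups |
| Section 11.2 | Invitation; letter; telephone contact; information package | All eligible patients |
| Section 4.2 | Phone check when inclusion starts; consent required | Both groups |
| Section 8.2 | Allocation, timing not stated | Both groups |

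1. **Baseline against inclusion.** If the numbered steps in Section 3 are chronological, which is their natural reading, baseline precedes the decision to participate. Section 8.3 puts it after inclusion. Both cannot be followed.

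2. **Where the decision sits.** In Section 3 the decision and inclusion occur only in step 2. Controls go from step 1 to step 5. Section 4.2 nevertheless requires their consent, and Section 11.2 recruits everyone by one route. Section 3 therefore does not describe how a control enters the study, and its step 2 does not fit Section 11.2.

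3. **Literal Section 3.** Sending only intervention patients to step 2 requires knowing who they are before they decide. Their decision then follows a meeting that controls do not have. Baseline comes before that meeting, so on this reading the meeting cannot colour it.

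4. **Section 3 combined with Section 8.3.** If the meeting and decision come first and the questionnaire follows inclusion, an intervention patient can complete baseline ESES already knowing the group. This arises only when the two sections are merged; neither states it alone.

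5. **Section 8.3 alone.** Baseline follows inclusion equally in both groups. Whether patients then know their group is left open.

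6. **Size.** A bias estimate would need the share of patients declining after the meeting and the difference in ESES change between those who accept and those who decline. The protocol gives neither. It states a target of 30 patients, with no split, standard deviation or effect size.

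**The case against.** The strongest reply is that this is loose drafting. Controls also consent (Section 4.2), and Section 11.2 informs all invited patients in the same way, so step 2 may simply describe the extra introduction for app users. Section 3 separately has both groups complete the questionnaire before the testing period, which fits either order. The process and timeline figures are not reproduced in the text available here and may settle the sequence. The study is a 30-patient pilot that openly concedes incomplete randomisation. Much of this stands, and it limits the point to an inconsistency with possible consequences.

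A reader might infer more than the document supports:

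- *That intervention patients try the app before deciding.* They receive information; installation and instruction in its use come after inclusion.
- *That the group is assigned before consent.* No section times allocation. This follows only if Section 3 is taken literally.
- *That selection and baseline do differ between groups.* Each section applies its own baseline order to both groups alike, and Section 11.2 recruits them together. The documents show only that differences can arise.
- *That the bias can be sized from assumed refusal rates and ESES gaps.* Nothing in the protocol anchors such inputs. A stable gap in ESES level would also cancel in the before-after comparison of Section 10.1.
- *That refusals will be hidden.* Nothing says they will go unrecorded.

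The reply does not remove the conflict. Section 11.2 is a further sequence that neither mentions nor replaces the step 2 meeting, and pilot status does not explain why the order of consent and baseline should differ between sections.

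**Conclusion.** The point holds as an inconsistency that should be corrected. Sections 3 and 8.3 contradict each other on whether baseline ESES comes before or after inclusion, provided the numbered steps are chronological. Section 3's decision step, which only the intervention group passes through, does not fit the common route in Section 11.2, and allocation is not placed relative to consent or baseline anywhere.

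The consequences are conditional. Literal use of Section 3 can add selection beyond the NFC-phone criterion. Merging it with Section 8.3 can let patients complete baseline ESES knowing their group. The magnitude of either effect is unknown and cannot be calculated from this document.

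**What to change.** State one sequence, in the same terms, in Sections 3, 8.3 and 11.2 for both groups:

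1. NFC-phone check.
2. Common information and consent.
3. Baseline ESES.
4. Allocation revealed, randomised among patients who have an NFC phone.
5. Technology introduction, for the intervention group only.

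Keep every allocated patient in the comparison, and count those who decline the app after allocation. Section 8.6 already asks patients who stop to complete the end measurements unless they want their data deleted, so this fits existing procedures.

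The cost is re-ordering and aligned wording, with no added visit. There are two downsides. A few allocated patients may never start the app yet remain in the comparison. Patients without an NFC phone can still infer that they will be controls, so knowledge of the group at baseline is reduced but not removed.

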4. STUDY POPULATION

4.1 Population (base)

This study will include patients that, within their rehabilitation program, receive frequent physical therapy exercises to perform at home. These patients will be recruited from their rehabilitation by physiotherapists from within the Radboudumc. We will recruit patients with distinct situations, namely Neuralgic Amyotrophy and a lower extremity amputation who use a socket prosthesis or an osseointegrated prosthesis.

4.2 Inclusion criteria

In order to be eligible to participate in this study, a subject must meet all of the following criteria:

Intervention group:

- Willing to participate and to provide informed consent
- Minimal remaining rehabilitation period of 4 weeks
- Access to NFC-compatible smartphone
- Within their rehabilitation program, included patients have exercises to perform at home.
- Patient is able to speak, read and understand Dutch

Control group:

- Willing to participate and to provide informed consent
- Minimal remaining rehabilitation period of 4 weeks
- Within their rehabilitation program, included patients have exercises to perform at home.
- Patient is able to speak, read and understand Dutch

These inclusion criteria show that patients who are excluded from the intervention group can be included in the control group. Therefore, patients will be asked whether they have a NFC-compatible smartphone at the start of inclusion. At this point, most Android smartphones are NFC-compatible. This makes the study not truly randomized, but seems reasonable as this is a pilot study.

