4.4 Sample size calculation

This project primarily aims to provide an insight and preliminary evaluation of utilizing NFC-equipped stickers to increase self-efficacy in home exercise programmes. As this is an exploratory pilot study, no formal power analysis has been conducted. We aim to include 30 patients spread across control and intervention group. This includes patients with a lower extremity amputation and Neuralgic Amyotrophic patients. If the pilot is successful, the data provided can be used to expand the research and calculate a sample size for randomized controlled trials.

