6. INVESTIGATIONAL PRODUCT

6.1 Name and description of investigational product(s)

To address the self-efficacy and to empower patients in performing exercises, Radboud REshape is developing an innovative intervention in close collaboration with a company called Touchless Industries. Together, they came up with a sticker, equipped with the recently developed NFC technology. NFC is a technology that has emerged and is still growing in availability. Estimates by Statista (one of the world's leading statistics portals gathering data from more than 18.000 sources) show a expected number of 1.9 billion NFC-enabled smartphones in 2018 (Statista, 2013). However, this includes Apple iPhones, whose NFC technology is not freely accessible by all apps. IHS Markit (claiming to be the leading source of information, insight and analytics in critical areas that shape today's technology ecosystem) has estimated that by 2018, 844 million, or 75 percent of Android phones will be equipped with accessible NFC technology (IHS, 2014). Furthermore, mobile network providers (such as the Dutch provider KPN) have started to equip their SIM cards with NFC technology, which supersedes the need for NFC technology on the mobile device itself (KPN, n.d.). Thus, although the market is still growing, a wide availability for NFC smartphones shall be present in the near future.

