8.2 Randomisation, blinding and treatment allocation

We will randomise the allocation of patients to study groups as much as possible within the patient (and NFC) availability pool. Blinding is not appropriate for this pilot.

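### NFC phone access is required for the intervention arm only, so it is partly confounded with treatment in the primary self-efficacy comparison

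*Protocol*

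**What the plan says.** Section 4.2 gives each arm its own inclusion list. The lists match except for one item, "Access to NFC-compatible smartphone", which applies to the intervention group alone. The protocol draws the consequence itself: "These inclusion criteria show that patients who are excluded from the intervention group can be included in the control group". It then comments: "This makes the study not truly randomized, but seems reasonable as this is a pilot study".

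Section 8.2 is consistent with this: "We will randomise the allocation of patients to study groups as much as possible within the patient (and NFC) availability pool". No allocation ratio is given. Section 4.4 states only a total: "We aim to include 30 patients spread across control and intervention group". The intervention runs on the patient's own device, since section 3 says "the patient can scan the tag with their personal smartphone", and no loan phone is mentioned.

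Section 10.1 compares before and after ESES values within and between the control and intervention groups as wholes. Phone status is asked at the start of inclusion (4.2). It is not among the demographic variables in 8.1.3, 8.3 or 10.3, nor in the data table in 12.1, and no analysis in section 10 uses it.

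**The concern.** A patient without NFC access has no chance of receiving the intervention and can only be a control. The control arm is then a mixture of patients who could have been allocated either way and patients who could not, while the intervention arm holds only the first kind. A difference between arms may partly reflect who has such a phone. NFC access could plausibly go with age, education or ease with technology, and these could bear on how self-efficacy changes during rehabilitation.

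Pilot status does not settle the matter, because the protocol still puts the comparison to use. The primary objective (section 2) asks whether the reminders raise self-efficacy relative to usual care. Section 3 gives the control group the task of separating intervention effects from treatment effects. Section 8.1.2 counts the effect on self-efficacy as part of feasibility, and section 10 sets a significance threshold of 0.05. Controls who could never have used the product weaken each of these uses.

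**Working it through.** The protocol states no power or bias figure to reproduce ("As this is an exploratory pilot study, no formal power analysis has been conducted"). What follows is an illustration.

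**Inputs from the protocol**
- Total N = 30 (4.4), split not stated.
- Significance level 0.05 (section 10), taken as two-sided.
- A worldwide forecast in 6.1: "844 million, or 75 percent of Android phones will be equipped with accessible NFC technology".

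**Assumptions**
- q, the share of recruited patients with NFC access: 0.75 borrowed from that forecast, range 0.5 to 0.9.
- d, the difference in 4-week ESES change between patients with and without access, in SD units: 0.25, 0.5 and 0.8. The documents give no value.
- The between-group comparison is treated as a two-sample comparison of change.
- Two allocations. A: 15 per arm, with all patients without access in control. B: patients with access randomised 1:1, the rest added to control.

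**Step 1: share of controls without access**

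Patients without access = 30 × (1 − q). At q = 0.75 this is 7.5.
- A: 7.5 / 15 = 50%.
- B: the intervention arm has 30 × 0.75 / 2 = 11.25 and control has 11.25 + 7.5 = 18.75, so 7.5 / 18.75 = 40%.

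| q | A | B |
|---|---|---|
| 0.90 | 20% | 18% |
| 0.75 | 50% | 40% |
| 0.60 | 80% | 57% |
| 0.50 | 100% | 67% |

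The intervention arm has 0% throughout. Access and arm coincide completely only in the last row under A.

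**Step 2: bias and false-positive rate with no true effect, q = 0.75**

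Bias b = share × d. SE = √(1/n₁ + 1/n₂), which is √(2/15) = 0.365 for A and √(1/11.25 + 1/18.75) = 0.377 for B. Rejection rate = Φ(−1.96 + b/SE) + Φ(−1.96 − b/SE).

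| d | A: bias, rate | B: bias, rate |
|---|---|---|
| 0.25 | 0.125 SD, 6.4% | 0.10 SD, 5.8% |
| 0.5 | 0.25 SD, 10.5% | 0.20 SD, 8.3% |
| 0.8 | 0.40 SD, 19.5% | 0.32 SD, 13.6% |

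At q = 0.9 and d = 0.5 the rate is 5.7% to 5.9%, close to nominal.

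**Step 3: cost of restricting the comparison**

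At q = 0.75, about 22 of 30 patients (11 per arm) contribute. The 95% CI half-width is t × √(2/n):
- 15 per arm: 2.048 × √(2/15) = 0.75 SD.
- 11 per arm: 2.086 × √(2/11) = 0.89 SD.

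**The case against.** The strongest reply is that this is a disclosed trade-off in an exploratory pilot with no power claim. Disclosure is to the protocol's credit, but it does not change the comparison, and nothing in the design or analysis deals with the imbalance.

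Several further objections stand and limit the point:

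- **The size is not known.** A reader might infer from 6.1 that at least a quarter of these patients lack usable NFC, and hence that about half of the controls do. The 75% is a worldwide Android forecast. The same section says that iPhone NFC is not open to all apps, which lowers availability, and that NFC SIM cards can replace NFC in the handset, which raises it. So 25% is not a floor, and no 15:15 split is stated.
- **A stable difference cancels.** A reader might infer that any difference in self-efficacy between people with and without such phones biases the result. ESES is measured before and after in both arms, so a constant difference in level drops out of a comparison of change. Only a different 4-week course matters, and no document shows one.
- **Restriction does not clearly reduce total error.** Against 15 per arm, the smaller comparison has the lower mean squared error only if the bias exceeds √(2/11 − 2/15) = 0.22 SD. Its advantage is that phone access no longer explains a difference, not that the estimate is sure to be closer.
- **The data keep other uses.** A reader might infer that the pilot could not inform a later trial. Section 4.4 makes such a trial conditional on success, and usability, app use and interview findings do not depend on an unbiased group contrast.

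Two points help less. The exploratory tests on age and education (10.1, 10.3) are not adjustments of the primary comparison. A separate analysis plan, not seen here, could add phone status as a covariate, but with no patients without access in the intervention arm, those patients would inform the contrast only through model assumptions. Eligibility and allocation are fixed in the protocol.

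**Conclusion.** The point holds as partial confounding of NFC access with treatment in the primary between-group comparison. It follows directly from 4.2, 8.2 and 10.1. It would be complete only if about half of the patients or fewer had access and all of them were needed for the intervention arm.

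The magnitude is illustrative. With 75% access and an assumed 0.5 SD difference in change, the bias is 0.20 to 0.25 SD and the false-positive rate 8.3% to 10.5%. With 90% access, or a smaller difference in change, the effect is slight. With no difference in change there is no bias in change. The direction cannot be stated.

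This should be fixed. It does not invalidate the pilot, but as written the design leaves phone access as a rival explanation for any ESES difference, and the protocol has no step that would separate the two.

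**What to change.** - In 4.2, apply the NFC access criterion to both arms for the primary comparison.
- In 8.2, randomise only patients with NFC access.
- In 8.1.3 and the baseline questionnaire, record NFC access as a baseline variable. The question is already asked at inclusion, so this adds almost no work.
- In 10.1, base the between-group ESES comparison on the randomised patients with access. If usual-care patients without access are also followed, report them as a separate descriptive reference group outside that comparison.

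The cost is precision or time. If 22 rather than 30 patients contribute, the 95% CI half-width rises from about 0.75 to 0.89 SD. Keeping 30 in the comparison means finding more patients with NFC access, which may be hard within the April and May 2018 inclusion window in section 3. No stated power is lost, because none was set. The change has to be made before enrolment, since allocation cannot be redone afterwards.
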